8.3.6 Day 3 Safety Phone Call

Site staff are required to call the legally acceptable representative of each participant on Day 3 postdose in RSV Seasons 1 and 2 to inquire about the participant's safety, in particular, if any AESI (anaphylaxis/hypersensitivity events and rash events) and SAEs have occurred since Day 1 of that RSV season, in addition to reviewing any data entered into the eDiary, including information pertaining to potential injection-site AEs (redness, swelling, or

tenderness). The Sponsor will provide each site with a guidance document (or equivalent) outlining the questions to be asked during the phone call.

If Day 3 is not a business day, the phone call should occur on Day 2. If the first attempt on Day 3 in either RSV season is unsuccessful, site staff should try to call the legally acceptable representative an additional 2 times that same day. If the legally acceptable representative is unreachable on Day 3 in either RSV season, site staff should continue to try to contact at least 3 additional times within the following 7 days. Each attempt should be recorded on the log provided by the Sponsor (or equivalent).

If any respiratory infection symptoms (see Section 8.2.1) or suspected AESI (see Section 8.4.8) are reported, the participant should be brought to the site for further assessment, if applicable.

8.3.7 Clinical Laboratory Assessments

Refer to Appendix 2 for the list of clinical laboratory tests to be performed and to the SoA for the timing and frequency.

- All protocol-required laboratory assessments, as defined in Appendix 2, must be conducted in accordance with the laboratory manual and the SoAs.
- If laboratory values from nonprotocol-specified laboratory assessments performed at the institution's local laboratory require a change in study participant management or are considered clinically significant by the investigator (eg, SAE or AE or dose modification), then the results must be recorded in the appropriate CRF (eg, SLAB).
- For any laboratory tests with values considered clinically significantly abnormal during participation in the study or after the last dose of study intervention, every attempt should be made to perform repeat assessments until the values return to normal or baseline or if a new baseline is established as determined by the investigator.

8.4 Adverse Events, Serious Adverse Events, and Other Reportable Safety Events

The definitions of an AE or SAE, as well as the method of recording, evaluating, and assessing causality of AE and SAE and the procedures for completing and transmitting AE, SAE, and other reportable safety event reports can be found in Appendix 3.

Adverse events, SAEs, and other reportable safety events will be reported by the participant (or, when appropriate, by a caregiver, surrogate, or the participant's legally authorized representative).

The investigator and any designees are responsible for detecting, documenting, and reporting events that meet the definition of an AE or SAE as well as other reportable safety events. Investigators need to document if an SAE was associated with a medication error, misuse, or abuse.

Investigators remain responsible for following up AEs, SAEs, and other reportable safety events for outcome according to Section 8.4.3. The investigator, who is a qualified physician, will assess events that meet the definition of an AE or SAE as well as other reportable safety events with respect to seriousness, severity, and causality.

8.4.1 Time Period and Frequency for Collecting AE, SAE, and Other Reportable Safety Event Information

All AEs, SAEs, and other reportable safety events that occur after the participant's legally acceptable representative provides documented informed consent but before intervention randomization must be reported by the investigator if the event causes the participant to be excluded from the study, or is the result of a protocol-specified intervention.

All AEs, SAEs, and other reportable safety events must be reported by the investigator:

- From the time of intervention randomization through 14 days following RSV Season 1 Dose 2,
- For 14 days following each subsequent dose of palivizumab in RSV Season 1 (planned and additional post-surgery doses),
- For 42 days following the RSV Season 2 dose,
- For 42 days after an additional post-surgery dose of MK-1654 in either RSV season, and
- Any SAE through participant's study completion.

Additionally, any SAE brought to the attention of an investigator at any time outside of the time period specified in the previous paragraph must be reported immediately to the Sponsor if the event is considered related to study intervention.

Investigators are not obligated to actively seek AEs or SAEs or other reportable safety events in former study participants. However, if the investigator learns of any SAE, including a death, at any time after a participant has been discharged from the study, and the investigator considers the event to be reasonably related to the study intervention or study participation, the investigator must promptly notify the Sponsor.

All initial and follow-up AEs, SAEs, and other reportable safety events will be recorded and reported to the Sponsor or designee within the time frames as indicated in [Table 3](#).

Table 3 Reporting Periods and Time Frames for Adverse Events and Other Reportable Safety Events

Type of Event	Reporting Time Period: Consent to Randomization/ Allocation	Reporting Time Period: Randomization/ Allocation through Protocol- specified Follow-up Period	Reporting Time Period: After the Protocol-specified Follow-up Period	Time Frame to Report Event and Follow-up Information to Sponsor:
Nonserious Adverse Event (NSAE)	Report if: - due to protocol-specified intervention - causes exclusion	Report all	Not required	Per data entry guidelines
Serious Adverse Event (SAE)	Report if: - due to protocol-specified intervention - causes exclusion	Report all	Report if: drug/vaccine related. (Follow ongoing to outcome)	Within 24 hours of learning of event
Pregnancy/Lactation Exposure	Not applicable since participants are infants.			
Event of Clinical Interest (require regulatory reporting)	There are no events of clinical interest for this study.			
Event of Clinical Interest (do not require regulatory reporting)	There are no events of clinical interest for this study.			
Adverse Event of Special Interest (AESI)	Report if: - due to intervention - causes exclusion	Report all	Report Serious AESI in the same manner as SAE	Within 5 calendar days of learning of event (unless serious)
Cancer	Report if: - due to intervention - causes exclusion	Report all	Report Serious Cancer in the same manner as SAE	Within 5 calendar days of learning of event (unless serious)
Overdose	Not applicable	Report all	Not required	Within 5 calendar days of learning of event

AESI=adverse event of special interest; ECI=event of clinical interest; NSAE=nonserious adverse event; SAE=serious adverse event

8.4.2 Method of Detecting AEs, SAEs, and Other Reportable Safety Events

Care will be taken not to introduce bias when detecting AEs and/or SAEs and other reportable safety events. Open-ended and nonleading verbal questioning of the participant is the preferred method to inquire about AE occurrence.

8.4.3 Follow-up of AE, SAE, and Other Reportable Safety Event Information

After the initial AE/SAE report, the investigator is required to proactively follow each participant at subsequent visits/contacts. All AEs, SAEs, and other reportable safety events, including pregnancy and exposure during breastfeeding, ECIs, cancer, and overdose will be followed until resolution, stabilization, until the event is otherwise explained, or the participant is lost to follow-up (as defined in Section 7.3). In addition, the investigator will make every attempt to follow all nonserious AEs that occur in randomized participants for outcome. Further information on follow-up procedures is given in Appendix 3.

8.4.4 Regulatory Reporting Requirements for SAE

Prompt notification (within 24 hours) by the investigator to the Sponsor of SAE is essential so that legal obligations and ethical responsibilities towards the safety of participants and the safety of a study intervention under clinical investigation are met.

The Sponsor has a legal responsibility to notify both the local regulatory authority and other regulatory agencies about the safety of a study intervention under clinical investigation. The Sponsor will comply with country-specific regulatory requirements and global laws and regulations relating to safety reporting to regulatory authorities, IRB/IECs, and investigators.

Investigator safety reports must be prepared for SUSARs according to local regulatory requirements and Sponsor policy and forwarded to investigators as necessary.

An investigator who receives an investigator safety report describing an SAE or other specific safety information (eg, summary or listing of SAE) from the Sponsor will file it along with the IB and will notify the IRB/IEC, if appropriate according to local requirements.

8.4.5 Pregnancy and Exposure During Breastfeeding

Information in this section is not applicable, as participants are infants.

8.4.6 Disease-related Events and/or Disease-related Outcomes Not Qualifying as AEs or SAEs

Not applicable for this study.

8.4.7 Events of Clinical Interest

Not applicable; there are no ECIs defined for this study.

8.4.8 Adverse Events of Special Interest

All AESI occurring from Day 1 through 14 days post Dose 2 in RSV Season 1 and within 42 days postdose in RSV Season 2 will be reported to the Sponsor. In addition, participants who receive an additional post-surgery dose of MK-1654 in either RSV Season 1 or 2 will be followed for 42 days postdose. Only AESI that occur outside these safety follow-up periods that meet the SAE criteria (see Section 10.3.2) should be reported to the Sponsor.

The investigator will provide an assessment of severity for AESI according to the grading scales provided in both Section 10.3.4 and the Severity Grading for Adverse Events document, which are based on an adaption of the NCI CTCAE, version 5.

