A prophylactic mAb targeting the RSV F protein, palivizumab (Synagis™, MedImmune), is approved for the prevention of serious lower respiratory tract disease caused by RSV in children at high risk for RSV disease and with medical conditions that place them at risk of complications from this disease [U.S. Prescribing Information 2009] [American Academy of Pediatrics Committee on Infectious Diseases 2014]. In the published controlled study of the IMPact-RSV Study Group, palivizumab reduced RSV hospitalization by approximately 55% compared to placebo in premature and high-risk infants (≤ 35 weeks gestation and ≤ 6 months of age; or ≤ 24 months with a clinical diagnosis of CLD (also referred to as bronchopulmonary dysplasia) requiring ongoing medical treatment within the past 6 months) [Joffe, S., et al 1999] [The IMPact-RSV Study Group. 1998]. However, the infant population in which palivizumab is recommended has narrowed due to limited clinical benefit and high cost [American Academy of Pediatrics Committee on Infectious Diseases 2014]; monthly

dosing to cover the entire RSV season also limits the wide use of palivizumab. A highly potent mAb with extended half-life, like MK 1654, with a one-time administration given during the first RSV season would address an unmet need. Moreover, a fully human mAb administered only once (eg, MK-1654) should display a relatively lower incidence of hypersensitivity reactions compared with a humanized mAb that is given multiple times throughout the RSV season.

Refer to the IB for detailed background information on MK-1654.

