the Fc domain only, and has no endogenous target in humans (refer to the IB for additional details). Administration of MK-1654 as a single injection or 2 divided-dose injections on the same day in ongoing and planned clinical studies further reduced the risk of hypersensitivity events, which were largely seen with re-exposure to palivizumab or motavizumab after multiple monthly doses. Administration of MK-1654 has been generally well tolerated in ongoing clinical studies in healthy infant participants (PN002) and in healthy Japanese adult male participants at doses up to 300 mg IM and 1000 mg IV (PN003), with no study pause rules triggered at any point in either study (see Section 2.2.3).

Additional details regarding specific benefits and risks for participants participating in this clinical study may be found in the accompanying IB and informed consent documents.

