- Day 1 through 14 days post Dose 2,
- For 14 days after each dose of palivizumab, and
- For 42 days after an additional post-surgery dose of MK-1654 or for 14 days after an additional post-surgery dose of palivizumab (see Section 8.1.8.1)

7. Concomitant medications and nonstudy vaccinations:

- Day 1 through 14 days post Dose 2, and

- For 42 days after an additional post-surgery dose of MK-1654 (see Section 8.1.8.1)

Legally acceptable representatives will use the eDiary to record the following information in RSV Season 2:

1. Solicited daily body temperature to identify fever* occurring within 5 days postdose;

***Note:** Fever is defined as rectal temperature $\geq 102.2^{\circ}\text{F}$ ($\geq 39.0^{\circ}\text{C}$) or axillary temperature $\geq 101.7^{\circ}\text{F}$ ($\geq 38.7^{\circ}\text{C}$).

2. Solicited injection-site AEs (redness/erythema, swelling, and tenderness/pain)** are collected within 5 days postdose;

****Note:** Injection-site AEs of redness/erythema and swelling will be measured by the legally acceptable representative using a study-supplied ruler.

3. Solicited systemic AEs (irritability, drowsiness, and appetite lost) for 5 days after each dose;
4. Anaphylaxis/hypersensitivity AESI occurring within 42 days after the RSV Season 2 dose and after an additional post-surgery dose of MK-1654 (see Section 8.1.8.1);
5. Rash AESI occurring within 42 days after the RSV Season 2 dose and after an additional post-surgery dose of MK-1654 (see Section 8.1.8.1);
6. Any other AEs occurring within 42 days after the RSV Season 2 dose and after an additional post-surgery dose of MK-1654 (see Section 8.1.8.1); and
7. Concomitant medications and nonstudy vaccinations occurring within 42 days after the RSV Season 2 dose and after an additional post-surgery dose of MK-1654 (see Section 8.1.8.1).

If any respiratory infection symptoms are reported that might require further assessment, the site staff should call the legally acceptable representative to ascertain additional information and arrange a site visit if needed (see Section 8.2.1 and Section 8.2.2).

The investigator will use the information provided by the participant's legally acceptable representative, both from the eDiary and verbally at the time of eDiary review, to provide an assessment for severity of AEs (see Section 10.3.4).

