9.6.2 Statistical Methods for Safety Analyses

Safety and tolerability will be assessed by clinical review of all relevant parameters including AEs. All safety summaries will be provided separately for the participants' first and second

RSV seasons. Comparisons between the 2 groups will be made in RSV Season 1 only. The primary comparison of safety endpoints in RSV Season 1 will be after the first 2 doses in each group, ie, after the MK-1654 and placebo doses versus after the first 2 palivizumab doses. A supplemental comparison of safety endpoints in RSV Season 1 will be after the MK-1654 and placebo doses versus after all doses in the palivizumab group.

The analysis of safety results will follow a tiered approach (Table 7). The tiers differ with respect to the analyses that will be performed. AEs (specific terms as well as SOC terms) and events that meet PDLCS in laboratory and vital signs parameters are either prespecified as “Tier 1” endpoints or will be classified as belonging to “Tier 2” or “Tier 3” based on the observed proportions of participants with an event.

Tier 1 Events

Safety parameters or AEs of particular interest that are identified a priori constitute “Tier 1” safety endpoints that will be subject to inferential testing for statistical significance. There are no Tier 1 events for this protocol as no treatment-related SAEs have been observed in the Phase 1 studies of MK-1654.

Tier 2 Events

Tier 2 parameters will be assessed via point estimates with 95% CIs provided for differences in the proportion of participants with events (via the unstratified Miettinen and Nurminen method [1985]).

Membership in Tier 2 requires that at least 1% of the participants in any treatment group have the event. All other AEs will belong to Tier 3. Maximum body temperature will be summarized using Brighton Collaboration cutoffs.

The threshold of at least 1% was chosen to draw clinical meaningful inference. When less than 1% of participants report AEs in both groups, the 95% CI for the between-group difference may exclude zero. However, the clinical significance of these differences is unknown given the small number of participants who report AEs. Because many 95% CIs for Tier 2 events may be provided without adjustment for multiplicity, the CIs should be regarded as a helpful descriptive measure to be used in review, not a formal method for assessing the statistical significance of the between-group differences in AEs.

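### Nonserious hypersensitivity and rash after palivizumab Doses 3-5 are recorded only as ordinary AEs, so the supplemental all-dose AESI comparison is incomplete and Section 8.4.8 conflicts with Section 8.4.1 and Table 3

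*Combined protocol and SAP*

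**What the plan says.** The Season 1 AESI window in Section 8.4.8 covers "All AESI occurring from Day 1 through 14 days post Dose 2 in RSV Season 1". After it, the rule is "Only AESI that occur outside these safety follow-up periods that meet the SAE criteria (see Section 10.3.2) should be reported to the Sponsor". The only Season 1 extension is 42 days after a post-surgery dose of MK-1654; a post-surgery dose of palivizumab has none. The eDiary rules in Section 8.3.5 (Season 1 items 4 and 5), the call and visit triggers in Sections 8.4.8.1 and 8.4.8.2, the two AESI endpoints in Section 9.4.2 and footnote b of Table 7 all use the same cut-off.

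General AE reporting runs longer. Section 8.4.1 requires AEs, SAEs and other reportable safety events "For 14 days following each subsequent dose of palivizumab in RSV Season 1 (planned and additional post-surgery doses". Table 3, in the same section, has an AESI row: all are to be reported through the follow-up period that the protocol specifies, and after that period the entry is "Report Serious AESI in the same manner as SAE".

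On the expected risk, Section 2.3 says of hypersensitivity events "which were largely seen with re-exposure to palivizumab or motavizumab after multiple monthly doses". Section 2.2 adds that a fully human antibody given once "should display a relatively lower incidence of hypersensitivity reactions compared with a humanized mAb that is given multiple times throughout the RSV season".

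On analysis, Section 9.6.2 makes the first two doses in each group the primary safety comparison. It adds a supplemental comparison of safety endpoints after MK-1654 and placebo "versus after all doses in the palivizumab group".

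**The concern.** The AESI window takes in one palivizumab re-exposure (Dose 2) and then closes, although the documents link the risk to repeated monthly dosing. Two consequences follow.

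First, a site that sees nonserious urticaria the day after Dose 4 has two instructions. Section 8.4.1 with Table 3 points to reporting it, including as an AESI. Section 8.4.8 limits AESI reporting at that time to serious events. Different sites could apply different rules.

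Second, the supplemental comparison is meant to cover every palivizumab dose. For AESI, nonserious events after Doses 3-5 would be missing because of the collection rule, not because they did not occur. A reader of that table would see an all-dose label over what is, for nonserious AESI, a two-dose count.

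**Working it through.** **The plan's own figure.** Days 1-42 is defined as Day 1 through 14 days after Dose 2. Dose 2 at Day 28 plus 14 days gives Day 42. With the +4-day dosing window it can run to Day 46, which matches the Day 42 (+4) contact in the Section 1.3.1.1 schedule. The figure reproduces.

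**The passages side by side, for a nonserious Table 4 or Table 5 event within 14 days of palivizumab Doses 3-5.**

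- Section 8.4.1: within a reporting period, so reportable.
- Table 3, AESI row: report all, if the follow-up period is the one set out in Section 8.4.1.
- Section 8.4.8: outside the AESI period, so reportable as an AESI only if serious.
- Section 8.3.5: outside items 4 and 5 (AESI), inside item 6 (any other AE).
- Section 8.3.4 with the schedule in Section 1.3.1.3: the 30-minute observation looks for immediate anaphylaxis/hypersensitivity and rash, refers to the AESI sections, and is scheduled at Doses 3-5.
- Section 1.3.1.3: the header lists unscheduled visits for AESI assessment, but there is no AESI assessment row.
- Section 9.4.2: of seven primary safety endpoints, five run after every dose or through the season; only the two AESI endpoints stop after Dose 2.

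**Share of palivizumab doses outside the AESI window.** Inputs: k = 3 to 5 doses (Section 2.2.4) and 500 palivizumab infants (Section 2.3), assuming every infant receives all k doses. The share is (k - 2)/k.

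| k | Share outside | Injections outside, of total |
|---|---|---|
| 3 | 1/3 = 33% | 500 x 1 = 500 of 1500 |
| 4 | 2/4 = 50% | 500 x 2 = 1000 of 2000 |
| 5 | 3/5 = 60% | 500 x 3 = 1500 of 2500 |

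**Share of dose-linked AE collection days without AESI collection.** Nominal AE days are 42 + 14(k - 2), of which 42 carry AESI collection. The share without it is 14/56 = 25%, 28/70 = 40% and 42/84 = 50% for k = 3, 4 and 5.

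**Illustration in events.** The documents give no AESI rate, so the per-dose risk q is an assumption, varied from 0.1% to 1%. With equal risk per dose, the share of palivizumab infants with an AESI whose only AESI come after Dose 2 is 1 - [1 - (1 - q)^2] / [1 - (1 - q)^k].

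- q = 0.1%: in 500 infants, about 1.0 expected with an event inside the window, against 1.5 (k = 3) or 2.5 (k = 5) over all doses; shares 33.3% and 59.9%.
- q = 1%: about 9.95 inside, against 14.85 or 24.50; shares 33.0% and 59.4%.

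If the per-dose risk doubles after Dose 2, again an assumption, the share of events is 2(k - 2)/[2 + 2(k - 2)]: 2/4 = 50% for k = 3 and 6/8 = 75% for k = 5. Serious events stay reportable, so each share is an upper bound on the loss under its assumption.

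**The case against.** The strongest case against has five parts.

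- **The events are not lost.** A reader might infer that AESI after Doses 3-5 are never captured. The documents do not support that. Serious AESI remain reportable under both Section 8.4.8 and Table 3. Nonserious events are collected as AEs for 14 days after each dose, with diary review and a follow-up call, and Section 10.3.5 has every AE graded for severity. What is missing is their identification as AESI. This stands, and it limits the point.
- **Table 3 may not conflict.** Its follow-up period could be read as the AESI period in Section 8.4.8, and the list of other reportable events in Section 8.4.3 does not name AESI. That reading is available. However, Table 3 sits in Section 8.4.1, whose reporting periods include the later palivizumab doses, and Table 3 has its own AESI row. The text does not settle which reading governs.
- **The two-dose window is deliberate.** Section 4.2.3 gives the placebo at Day 28 to hold the blind for 42 days, and Dose 2 is already a re-exposure. This justifies the primary comparison. It does not explain the rest, since AESI are collected open-label after the Season 2 dose and after a post-surgery MK-1654 dose, but not after a post-surgery palivizumab dose.
- **The supplemental comparison may not include AESI.** Section 9.6.2 refers to safety endpoints in general and neither includes nor excludes them. The plan should say.
- **Collecting more would bias the other way.** AESI identified open-label in the palivizumab arm alone would raise the comparator's count. Table 4 includes wheezing, dyspnea and bronchospasm, which may reflect underlying lung or heart disease. This stands, and it is why the added counts can only be descriptive.

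**Conclusion.** The concern holds in limited form. Under Section 8.4.8, the eDiary rules and the AESI endpoints, nonserious hypersensitivity and rash events are not identified as AESI after 33% to 60% of each infant's palivizumab doses (500 of 1500 to 1500 of 2500 injections if all 500 infants complete dosing), nor after a post-surgery palivizumab dose outside the window. The passages need reconciling, and any AESI count in the supplemental all-dose comparison is incomplete for palivizumab. The dose shares follow directly from the protocol; the event shares rest on assumed risks.

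Two stronger conclusions that a reader might draw are not supported. One is that the safety comparison is tilted towards MK-1654. The primary comparison uses the same blinded two-dose window in both arms and is untouched, and undercounting palivizumab events in the supplemental comparison works against MK-1654. The other is that the trial fails to test its own claim about single dosing. Sections 3 and 9.3 state that there are no hypotheses, and the statements in Sections 2.2 and 2.3 are rationale, not objectives.

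**What to change.** - Reconcile Sections 8.4.8, 8.4.8.1, 8.4.8.2 and 8.3.5 (items 4 and 5) and the Section 1.3.1.3 schedule with Section 8.4.1 and Table 3. Events matching Table 4 or Table 5 terms within 14 days of each palivizumab dose after Dose 2, including post-surgery doses, should be identified as AESI. The minimum is to flag those terms in the AE data already collected. Extending the full AESI work-up is a separate and more debatable decision; the additional blood draw for Grade 3-4 events, for example, tests only for antibodies to MK-1654.
- Keep the blinded two-dose AESI comparison as primary.
- State in Section 9.6.2 that the supplemental analysis reports AESI after Doses 3-5 by dose number, labelled open-label, one-arm and descriptive, and not to be read as an unbiased between-group difference.
- Correct the reference for SAE criteria in Section 8.4.8 from 10.3.2, which defines an AE, to 10.3.3.

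The cost is wording in these sections, one schedule row and a flagging rule. Diary review, the 14-day calls, weekly contacts and AE collection already run in these periods. The price in interpretation is that identification is open-label and in one arm, and respiratory terms will pick up some underlying disease.
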